--	--

	
independence is not confirmed, the primary efficacy endpoint will be analyzed at the subject level. The primary efficacy analysis will then be a dichotomized Chi-square Responder analysis at the subject level. It will be based on the proportion of subjects considered to be Responders, where a Responder is defined as a subject for whom at least 5 treated tumors showing the greatest tumor-level percent reduction from baseline volume have a percent reduction from baseline volume of at least 50%. A Chi-square analysis with contrasts as outlined above will be used. At the subject level analysis, an Analysis of Variance will also be used to analyze the per-subject mean percent of tumor responders, with contrasts as described above. Treatment groups may also be compared using appropriate mixed-model logistic regression incorporating both tumor- and subject-level information. Supplementary analyses similar to those described above will also be conducted based on threshold reductions from baseline volume of at least 25%, 30%, 60% and 75%.
 
The first secondary efficacy endpoint will analyze the clinical efficacy of NFX-179 Gel defined as the mean percent change in neurofibroma volume after 182 days of treatment based on tumor volume derived from ruler measurements. Analyses of Variance will be conducted both on the tumor level and the subject level, including the contrasts as described above. The determination of whether the tumor-level or subject-level analysis will be considered primary will be based on the outcome of the tumor independence assessment as described above. The non-primary analysis will be considered as a supplementary analysis.
 
Additional secondary efficacy endpoints include the analysis of change from baseline in the Physician’s Tumor Assessment grades and the Subject’s Self-Assessment grades after 182 days of treatment. These will be analyzed analogously to the primary endpoint using an Analysis of Variance and contrasts describe above. In addition, for each assessment dichotomized analyses will be conducted on the proportion of tumors achieving a grade of Clear, the proportion of tumors achieving a grade of either Clear or Almost Clear, and also the proportion of tumors achieving at least a 1 grade, and also a 2 grade or greater improvement from baseline after 182 days of treatment. Treatment groups will be compared using separate Chi-square analyses. An appropriate mixed-model logistic regression may also be used, as well as an ANOVA of within-subject averaged results across tumors. Contrasts as described above will be used.
 
Analyses similar to those described above will be conducted based on changes and percent changes in tumor area, height, width and length.
 
Efficacy analyses at post-baseline visits prior to Day 182 where efficacy data are collected will also be performed using the models described above. These will be considered exploratory in nature.
 
Safety Analyses:

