7.2.1 Target cNF dimensions

At Visits 1, 2 (prior to the first study medication application), 4, 5, 6, 7, 8 and 9 the investigator will measure the length, width, and height above surrounding skin, in millimeters (mm) of each Target cNF using the ruler provided by NFlection Therapeutics, Inc.

At Visits 1 and 2, to be enrolled in the study a subject's Target cNFs located on the face must each have a length $\geq 5\text{mm}$ and $\leq 14\text{mm}$, a width $\geq 5\text{mm}$ and $\leq 14\text{mm}$ and a height $\geq 2\text{mm}$. Target cNFs located on the anterior trunk or upper extremities must each have a length of $\geq 7\text{mm}$ and $\leq 14\text{mm}$, a width of $\geq 5\text{mm}$ and $\leq 14\text{mm}$ and a height of $\geq 2\text{mm}$.

The investigator must report the following dimensions to the nearest 0.5mm using the half-millimeter graduated side of the ruler:

1. Determine if a clinically visible cNF tumor meets the inclusion criteria of the study protocol.

The identified area of the skin should be examined with a suitable examination light and may be used to determine whether the cNF tumor meets the inclusion criteria. No magnification can be used. Once it has been determined that a qualifying cNF tumor is present, measure the height, length, and width using the procedure described below:

2. Measure the height of the cNF tumor.

The cNF tumor should be examined with a suitable examination light. Cross lighting (tangential to cNF) may be used. Magnification may NOT be used.

[figure not shown]
The height of the cNF tumor should be measured at its highest point above the surrounding non-tumor skin. Use the ruler provided as illustrated below. The ruler should be gently placed on the non-tumor skin directly behind the cNF, perpendicular to the skin without creating a depression on the skin. Examine the visible cNF on a line parallel with the plane of the surrounding non-tumor skin and observe the ruler marking

at the highest point of the lesion. Report the cNF height to the nearest 0.5 mm using the half-millimeter graduated side of the scale.

As a guideline report the cNF tumor height as:

- **0mm:** define 0.5mm as the limit of detectability, therefore any cNF tumor <0.5mm will be rated as 0mm
- **0.5mm:** define 0.5mm as any cNF tumor that is $\geq 0.5\text{mm}$ and $< 1.0\text{mm}$
- **1.0mm:** define 1.0mm as any cNF tumor that is $\geq 1.0\text{mm}$ and $< 1.5\text{mm}$

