7.2.2 Physician's Tumor Assessment (PTA)

The PTA is the investigator's assessment of the average overall severity of each Target cNF at a particular time point. The investigator should NOT refer to any other assessments to assist with these assessments.

At Visits 1, 2 (prior to randomization), 4, 5, 6, 7, 8 and 9, the investigator will conduct the PTA for each Target cNF using the scale below and report the one integer that best describes the average overall severity of each Target cNF. The investigator must complete the PTA after the subject completes the SSA at the visit and prior to the first study medication application at Visit 2.

Physician's Tumor Assessment	
Grade	Descriptor
0	Clear/None: no visible cNF (perceptible pigmentary changes may be present)
1	Almost Clear: a slightly visible cNF above the surrounding skin
2	Mild: a noticeably visible/raised dome-shaped cNF
3	Moderate: a moderately raised dome shaped cNF
4	Severe: a significantly raised dome shaped cNF

If during the treatment phase a Target cNF clears (*i.e.*, PTA grade of 0) the subject should continue QD application to the area of the cNF for the remainder of the treatment period.

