9.3.4 Baseline Assessment

Descriptive statistics will be performed on relevant Visit 1 and Visit 2 data (*i.e.*, data collected prior to the treatment administration) and on demographic and baseline disease severity characteristics. There will be no statistical hypothesis testing of baseline data.

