9.3.5 Efficacy Analyses

9.3.5.1 Overview

Analyses of efficacy parameters collected at the tumor level will primarily be performed at the tumor level, under the assumption that tumor responses within the same subject will be predominantly statistically independent. Those parameters include results based on tumor dimensions, SSA and PTA evaluations, and responder analyses based on any of these measures. This approach is consistent with the topical application of the study medication to individual tumors and the assumption of minimal systemic absorption or systemic action of the study medication. The statistical assumption of within-subject tumor response independence will be evaluated using the appropriate Shrout-Fleiss intraclass correlation based on tumor changes from

baseline. For this study, that statistic is assumed to be less than 0.25. If this assumption is confirmed, analyses conducted at the subject level will then be performed as supplementary analyses. Tumor volume is the primary measurement of interest; however, the ruler measurements of tumor area, length, width and height will also be analyzed as supplementary analyses, using the analysis models applied to tumor volume.

If the Shrout-Fleiss intraclass correlation statistic is equal to or greater than 0.25, then subject-level efficacy parameter analyses will be considered primary, and tumor-level efficacy parameter analyses will be considered supplementary. In either case, results from both types of analyses will be presented.

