for whom at least 5 treated tumors showing the greatest tumor-level percent reduction from baseline volume have a percent reduction from baseline of at least 50%. A Chi-square analysis with contrasts as outlined above will be used. At the subject-level analysis, an Analysis of Variance will also be used to analyze the per-subject mean percent of tumor responders, with contrasts as described above. Treatment groups may also be compared using appropriate mixed-model logistic regression incorporating both tumor- and subject-level information. Supplementary analysis similar to those described above will also be conducted based on threshold reductions from baseline volume of at least 25%, 30%, 60% and 75%. The first secondary efficacy endpoint is to determine the clinical efficacy of NFX-179 Gel defined as the mean percent change in neurofibroma volume after 182 days of treatment based on tumor volume derived from ruler measurements. Analyses of Variance will be conducted both on the tumor level and the subject level, including the contrasts as described above. The determination of whether the tumor-level or subject-level analysis will be considered preferentially will be based on the outcome of the tumor independence assessment described above. The non-primary analysis will be considered as a supplementary analysis. Additional secondary efficacy endpoints include the analysis of change from baseline in the Physician's Tumor Assessment grade and the Subject's Self-Assessment grade after 182 days of treatment. These will be analyzed analogously to the primary endpoint using an Analysis of Variance and contrasts described above. In addition, for each assessment dichotomized analyses will be conducted on the proportion of tumors achieving a grade of Clear, the proportion of tumors achieving a grade of either Clear or Almost Clear, the proportion of tumors achieving at least a grade 1 improvement, and also a 2 grade or greater improvement from baseline after 182 days of treatment. Treatment groups will be compared using separate Chi-square analyses. An appropriate mixed-model logistic regression may also be used, as well as an ANOVA analysis of within-subject averaged results across tumors. Contrasts as described above will be used.

Analyses similar to those described above will be conducted based on tumor area and tumor length.

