9.5 Sub-Group Analyses

Exploratory efficacy investigations may be carried out based on subject gender, subject age, time since onset of NF1 diagnosis and/or cNF appearance, cNF classification, baseline tumor size, study medication compliance, and other factors.

Exploratory safety investigations may be carried out based on subject gender and age.

Exploratory sub-group analyses of safety parameters may be conducted based on time since CNF diagnosis, age at onset, study medication use per day, and other parameters.

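### The ANOVAs for percent change in volume and for PTA and SSA grade change omit the Visit 2 baseline: possible lost precision on secondary endpoints, not bias

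*Combined protocol and SAP*

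**What the plan says.** For percent change in volume, section 9.3.5.3 states: "Analyses of Variance will be conducted both on the tumor level and the subject level, including the contrasts as described above". For PTA and SSA grade change it states: "These will be analyzed analogously to the primary endpoint using an Analysis of Variance and contrasts described above". The Statistical Methods part of the synopsis says the same ("These will be analyzed analogously to the primary endpoint using an Analysis of Variance and contrasts describe above"). The contrasts in section 9.3.5.2 are between treatment groups only. The default level is set in section 9.3.5.1: "Analyses of efficacy parameters collected at the tumor level will primarily be performed at the tumor level". Subject-level analyses become primary if the intraclass correlation is 0.25 or more.

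The matching baselines exist. Section 7.2.1: "At Visits 1, 2 (prior to the first study medication application), 4, 5, 6, 7, 8 and 9 the investigator will measure" the tumor dimensions. Section 7.2.2: "At Visits 1, 2 (prior to randomization), 4, 5, 6, 7, 8 and 9, the investigator will conduct the PTA". Section 7.2.3 places the Visit 2 SSA before the first application, and section 6.2.2 lists all three measures among the steps done before randomization.

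No other section supplies a covariate:
- Section 9.3.1 allows parametric or nonparametric tests but names no adjustment.
- Section 9.3.4 uses baseline data descriptively ("There will be no statistical hypothesis testing of baseline data").
- Section 9.5 lists baseline size only among factors for optional exploratory investigations ("cNF classification, baseline tumor size, study medication compliance, and other factors").
- The optional mixed-model logistic regression is for dichotomized outcomes and names no baseline term.

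**The concern.** A change score is often related to its starting value, and several features of this trial make that plausible. On the 0 to 4 PTA scale a grade 2 tumor can improve by at most two grades and a grade 4 tumor by four. Entry thresholds for grade and size (sections 5.6.4 and 7.2.1) invite regression to the mean. Facial tumors may measure 5 to 14 mm in length and in width, so length times width can run from 25 to 196 mm², and dividing by baseline does not guarantee that percent change is unrelated to it. None of this gives the size of the relation.

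If the relation exists, an unadjusted ANOVA leaves explainable variance in the error term and leaves chance baseline imbalance in the treatment contrasts. At stake is the precision of all the listed secondary efficacy endpoints. Section 9.3.5.2 says the contrasts are meant to increase sensitivity, and a prespecified covariate serves that aim. Adding one after unblinding would make the choice of model depend on the data.

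**Working it through.** **The plan's own figure.** Section 9.1 states at least 90% power with about 168 randomized and 150 completing. The responder rates are redacted, so it cannot be reproduced. It concerns responders, not these ANOVAs.

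**Inputs.** From the documents: 50 completers per arm, three arms, 10 Target cNFs per subject, ICC threshold 0.25. Assumed, because the documents give none: every correlation, SD ratio and baseline ICC below.

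**1. Grade change, one value per subject.** Let r be the baseline/follow-up correlation and k the baseline SD over the follow-up SD, both the same in every arm. The variance ratio ANCOVA/ANOVA is (1 − r²)/(1 + k² − 2rk).

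| k | r = 0.3 | r = 0.5 | r = 0.6 | r = 0.9 |
|---|---|---|---|---|
| 0.6 | 0.91/1.00 = 0.91 | 0.75/0.76 = 0.99 | 0.64/0.64 = 1.00 | – |
| 0.8 | 0.91/1.16 = 0.78 | 0.75/0.84 = 0.89 | 0.64/0.68 = 0.94 | – |
| 1.0 | 0.91/1.40 = 0.65 | 0.75/1.00 = 0.75 | – | 0.19/0.20 = 0.95 |

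For PTA, k below 1 is plausible: entry requires grade 2 or more, while follow-up can fall to 0.

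**2. Percent change in volume, subject level.** With r now the correlation of baseline volume with percent change, the ratio is 1 − r²: 1.00, 0.96 and 0.75 at r = 0, 0.2 and 0.5.

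**3. Cost of one covariate.** With 150 subjects in three arms there are 147 residual degrees of freedom. The expected inflation is 1 + 1/(147 − 2) = 1.0069, about 0.7%. Adjustment loses slightly if the absolute correlation between baseline and the analysed change is below √(1 − 1/1.0069) = 0.083. For grade change that correlation is (r − k)/√(1 + k² − 2rk), so the loss zone is r = 0.53 to 0.66 at k = 0.6 and r = 0.74 to 0.84 at k = 0.8. At tumor level, with 1,500 independent tumors, the inflation is 1 + 1/1495 = 1.0007 and the break-even is about 0.026.

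**4. Chance imbalance.** The standard error of the difference in mean baseline between two arms is √(2/50) = 0.20 SD of the subject means. At tumor level it is √((2/500)(1 + 9 × ICC)): 0.063 SD at ICC 0 and 0.114 SD at ICC 0.25. For grade change, the fraction of any baseline difference passed into the unadjusted contrast is r/k − 1. At r = 0.5, k = 1 it is −0.5. At r = k it is zero.

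**5. Tumor-level model with correlated tumors.** Assume unit variances, both ICCs 0.25, 10 tumors per subject, and a correlation of baseline with the analysed change of 0.5 within subjects and 0 between subjects.
- Unadjusted variance of a subject mean: 0.25 + 0.75/10 = 0.325.
- Own baseline only: the pooled slope is 0.5 × 0.75 = 0.375, with square 0.1406. The variance is 0.25 + 0.1406 × 0.25 + (0.75 + 0.1406 × 0.75 − 2 × 0.375 × 0.375)/10 = 0.3426. The ratio is 0.3426/0.325 = 1.05, a loss (simulation 1.05).
- Own baseline plus subject mean: the correlation of subject means is 0.0375/0.325 = 0.115, and (1 − 0.115²) × 1.0069 = 0.99 (simulation 0.99).
- If the correlation is 0.5 both within and between subjects, own baseline alone gives 0.75.

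**6. In terms of power.** A comparison with 80% power under ANOVA at 50 per arm would have 81.6%, 83.6% or 89.9% at ratios of 0.96, 0.91 or 0.75, before the 0.7% cost.

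**The case against.** The strongest reply is that this is an optimisation. ANOVA on change is a valid randomized comparison, the endpoints are secondary in a Phase 2 study, and every gain rests on assumed values. That stands, and it limits the weight of the point. Three more specific objections also stand:
- The largest gains for grade change need k = 1, while the PTA entry rule points to k below 1, where the gain can vanish.
- Percent change in volume already divides by baseline. Its gain may be small, and nothing in the documents points to r = 0.5.
- Adjusting only for the tumor's own baseline, the obvious choice in the default tumor-level model, can lose precision. The remedy has to include the subject mean.

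The ratios in steps 1 and 2 also assume the same relation in every arm. An effective treatment that clears some tumors could change it.

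These objections reduce the expected gain but do not remove the case for adjusting. The subject-level cost is about 0.7% of variance and the data are already collected.

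**Conclusion.** The point holds as a low-cost improvement in precision, not as an error of validity. The plan names no baseline covariate for these three endpoints, and pre-treatment values are available for all of them. The gain cannot be fixed from the documents. Under the assumptions shown, the subject-level results run from no gain to a 35% reduction in variance for grade change, and from no gain to 25% for percent change in volume. Near-zero gains are credible for both.

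A reader might infer more, and the documents do not support it:
- That the ANOVA is biased or its type I error inflated by the missing covariate. Randomization rules this out on average.
- That the 90% power is overstated. It refers to the responder endpoint, which is not analysed by these ANOVAs.
- That the unadjusted contrast always carries baseline imbalance. It does so only when baseline is related to the analysed change; for grade change, none is carried when r = k.

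The primary responder analysis, the separate analyses by body location and the treatment of within-subject clustering are outside this point.

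**What to change.** In section 9.3.5.3 and the synopsis, replace ANOVA with ANCOVA for percent change in volume and for change in PTA and SSA grade, with the same contrasts.
- **Subject-level model:** adjust for the subject's mean Visit 2 baseline of the same measure over the Target cNFs.
- **Tumor-level model:** adjust for the tumor's own Visit 2 baseline and the subject's mean Visit 2 baseline.
- **Form:** enter each baseline, including grade, as a linear term.
- **Sensitivity analysis:** keep the unadjusted ANOVA.

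No new data are needed. The cost is one degree of freedom at subject level, two at tumor level, and a linearity assumption. That assumption applies to volume as well, since percent change already divides by baseline. The change is a wording amendment to the protocol and needs IRB/EC approval before use (section 12.1).

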5.2 Study Entry Criteria

5.2.1 Inclusion Criteria

To be eligible to participate in this study at Visit 1, the subject must fulfill all the following criteria:

1. Subject is at least 18 years of age
2. Subject must provide written informed consent prior to any study procedures

3. Subject must have a clinical diagnosis of NF1
4. Subject has 10 clinically diagnosed Target cNFs with preferably 2 Target cNFs located on the face and 8 Target cNFs located on the anterior trunk or upper extremities. Alternatively, at least 1 Target cNF is located on the face, in which case 9 Target cNFs must be located on the anterior trunk or upper extremities. Each Target cNF must meet the following criteria:
 - Has, in the investigator's opinion, a clinically typical appearance
 - Is not within 1 cm of the orbital rim
 - Is not covered with hair that might, in the investigator's opinion, interfere with obtaining photographs or impair evaluation of the cNF
 - Has a Physician's Tumor Assessment grade ≥ 2
 - Is dome shaped
 - Is not pedunculated
 - Is a discrete cNF surrounded by sufficient non-affected skin that, in the investigator's opinion:
 - i. The dimensions can be measured
 - ii. The perimeter can be outlined in the study photographs
 - Is not irritated (*e.g.*, bleeding, inflamed)
 - Is not in an area subject to repeated trauma (*e.g.*, area that is shaved, on the beltline, under a bra strap, etc.)
 - Does not have an active cutaneous infection
 - Target cNFs on the face must have the following tumor dimensions:
 - i. Has a length that is $\geq 5\text{mm}$ and $\leq 14\text{mm}$
 - ii. Has a width that is $\geq 5\text{mm}$ and $\leq 14\text{mm}$
 - iii. Has a height that is $\geq 2\text{mm}$.
 - Target cNFs on the anterior trunk or upper extremities must have the following tumor dimensions:
 - i. Has a length that is $\geq 7\text{mm}$ and $\leq 14\text{mm}$
 - ii. Has a width that is $\geq 5\text{mm}$ and $\leq 14\text{mm}$
 - iii. Has a height that is $\geq 2\text{mm}$
5. Subject agrees to minimize exposure of Target cNFs to sunlight and to use her/his routine sunscreen if exposure cannot be avoided
6. Subject agrees NOT to use tanning beds
7. Subject is willing to forego treatment of each Target cNF, except protocol specified therapy, during the study
8. Female subjects who are women of childbearing potential must have a negative urine pregnancy test result and be willing to use a protocol approved, contraceptive method for the duration of the study

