5.6.4 Subject randomization

At Visit 2, the investigator will determine the subject's eligibility for randomization to study medication. To be eligible for randomization the subject must:

- Have a PTA ≥ 2 for all Target cNFs
- Have clinical laboratory test results for all measured analytes at Visit 1 and all results are either within the range of normal for the laboratory or, any abnormal results, are defined as Not Clinically Relevant (NCR) by the investigator.
- Have, if a Woman of Childbearing Potential (WOCBP), a negative urine pregnancy test result at Visit 2.
- Have NOT used any topical or system therapies within the specified period prior to Visit 2 per the exclusion criteria

The investigator or designee will assign study medication to eligible subjects by selecting the

Subject Kits in chronological sequence in ascending numerical order starting with the lowest available Subject Kit number. The investigator will not omit or reuse any Subject Kit number.

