7.2.3 Subject's Self-Assessment (SSA)

The SSA is the subject's assessment of the average overall severity of each Target cNF at a particular time point, it is not a comparison with the SSA at any other time point. The subject should NOT refer to any other evaluation to assist with these assessments.

At Visits 2 (prior to the first study medication application), 4, 5, 6, 7, 8 and 9, each subject will evaluate each Target cNF using the scale below and report the one integer that best describes the average overall severity of the Target cNF. The subject must complete the SSA prior to the PTA at the visit and prior to the first study medication application at Visit 2.

To perform the SSA an investigational center staff member other than the investigator will complete the header on the SSA Scoring Report, provide the report to the subject and identify the first Target cNF to be evaluated. The staff member will identify the Target cNFs by Target cNF ID number, in ascending numerical order starting with the lowest available number. The staff member will then instruct the subject to perform the SSA for the first Target cNF using the scales below. This process of the staff member identifying a Target cNF and the subject performing the SSA will continue until the subject has performed the SSA for each of their Target cNFs. The staff member will collect the SSA Scoring Report and maintain it as a source document.

Subject's Self-Assessment	
Grade	Descriptor
0	Clear: no visible cNF
1	Almost Clear: a slightly visible cNF
2	Mild: a noticeably visible/raised cNF higher than the surrounding skin
3	Moderate: a moderately visible/raised cNF higher than the surrounding skin
4	Severe: a prominently visible/raised cNF higher than the surrounding skin

The subject will be allowed to take as much time as needed to complete the SSA.

The staff member must not influence the subject's assessment, explain the grades, or grade descriptors or in any way assist the subject with the SSA evaluations.

Both the subject and the staff member must initial and date the SSA Scoring Report to indicate that the evaluation was completed as instructed. The staff member will collect the SSA Scoring Report and maintain it as a source document.

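### The two absolute-grade SSA proportions (Clear; Clear or Almost Clear) have no baseline condition, so a tumor the subject already grades 0 or 1 at Visit 2 counts as a success without changing (minor)

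*Combined protocol and SAP*

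**What the plan says.** **Entry.** Each Target cNF needs a PTA grade of 2 or more at Visit 1 (5.2.1, 6.3). The randomization conditions in 5.6.4 repeat this: "Have a PTA ≥ 2 for all Target cNFs". Other tumor-level rules cover shape ("Is dome shaped", 5.2.1) and size: height at least 2 mm, width at least 5 mm, and length at least 5 mm on the face or 7 mm on the trunk and arms. Section 7.2.1 applies the size limits at Visits 1 and 2. No eligibility rule uses the SSA.

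**The SSA.** Section 7.2.3 gives the schedule: "At Visits 2 (prior to the first study medication application), 4, 5, 6, 7, 8 and 9, each subject will evaluate each Target cNF". The first grade is therefore the pre-treatment grade at Visit 2. The subject grades without consulting other evaluations and before the physician: "The subject must complete the SSA prior to the PTA at the visit". The scale runs from 0 (Clear) to 4 (Severe), and grade 1 reads "Almost Clear: a slightly visible cNF".

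**Analysis.** The SSA endpoint is change from baseline in grade, analysed by ANOVA (9.3.5.3). In addition, "for each assessment dichotomized analyses will be conducted on the proportion of tumors achieving a grade of Clear", then on the "proportion of tumors achieving a grade of either Clear or Almost Clear", and on improvement of at least 1 and at least 2 grades. The synopsis has the same list, including "the proportion of tumors achieving a grade of either Clear or Almost Clear". For the two absolute-grade proportions neither place excludes tumors already at those grades, requires a change, or adjusts for the Visit 2 grade.

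**The concern.** The same four dichotomies are applied to both scales, but the entry rule protects only one. On the PTA every tumor starts at 2 or higher, so a tumor at 0 or 1 after 182 days has improved by at least one grade. On the SSA a tumor may start at 0 or 1, stay there, and be counted among those that achieved Clear or Almost Clear.

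Two things are at stake. The reported SSA rates would include tumors on which treatment had nothing to show, which raises the rate in every arm and shrinks the difference between arms. The SSA rates would also sit beside PTA rates with the same label but a different meaning.

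A related, smaller matter is room to improve. A tumor starting at SSA 1 cannot improve by 2 grades, and one starting at 0 cannot improve at all. Such tumors are counted as failures, not false successes, in the improvement proportions, and they limit the change that the ANOVA can show.

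**Working it through.** **The plan's own figure.** The only power statement is at least 90% for the primary volume-responder comparison (9.1). Both responder rates are redacted, so it cannot be reproduced. The sizes agree with each other: 1 − 150/168 = 10.7% dropout. No power is stated for any SSA analysis, so what follows is an illustration and not a check of a stated number.

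**Inputs from the documents.** 50 completers per arm (synopsis), 10 Target cNFs per subject, two-sided alpha 0.05 (9.1).

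**Assumed inputs.** f is the share of tumors with Visit 2 SSA of 0 or 1, all taken to be at 0 or 1 again at Visit 8. True rates of reaching 0 or 1 among tumors starting at 2 or more are p = 10% (vehicle) and 25% (active). Within-subject correlation (ICC) is 0.2. None of these is in the documents.

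**Observed rate as written.** f + (1 − f)p in each arm. The f terms cancel in the difference, which becomes (1 − f)(0.25 − 0.10). At f = 10%:
- vehicle 0.10 + 0.90 × 0.10 = 0.190
- active 0.10 + 0.90 × 0.25 = 0.325
- difference 0.135, against 0.150 among tumors that could improve into these grades
- share of vehicle successes that never changed: 0.10/0.190 = 53%

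**Effective tumors per arm.** As written: 500/(1 + 9 × 0.2) = 178.6. Restricted to Visit 2 SSA of 2 or more, with m = 10(1 − f) tumors per subject: 50m/(1 + (m − 1) × 0.2). At f = 10%, m = 9 and this is 450/2.6 = 173.1.

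**Power**, two-proportion normal approximation:

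| f | Rates as written | Difference | Power as written | Power restricted |
|---|---|---|---|---|
| 2% | 11.8% v 26.5% | 14.7 points | 0.945 | 0.964 |
| 5% | 14.5% v 28.75% | 14.25 points | 0.908 | 0.962 |
| 10% | 19.0% v 32.5% | 13.5 points | 0.83 | 0.96 |
| 20% | 28.0% v 40.0% | 12.0 points | 0.67 | 0.95 |
| 30% | 37.0% v 47.5% | 10.5 points | 0.52 | 0.94 |

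The direction is the same at ICC 0.1 and 0.3.

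**Under the plan's own test.** With an ICC below 0.25 the plan uses a tumor-level chi-square that treats tumors as independent, so the design effect above is not part of it. Taking independence, 500 tumors per arm and a different assumed pair of rates (10% v 20%), power as written is 0.994 at f = 0, then 0.969, 0.920, 0.775 and 0.616 at f = 5, 10, 20 and 30%. Restricted, it is 0.991, 0.988, 0.978 and 0.961 at those same four values of f. In both settings restriction does better at every f above zero that was tried, despite the smaller denominator.

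**The case against.** The strongest reply concerns weight, not wording, and most of it stands.

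- **The stated SSA objective is not what is affected.** The objective and endpoint are change from baseline (section 3). The absolute-grade proportions are added analyses, and nothing is powered on them. A reader might infer that the SSA endpoint as a whole credits unchanged tumors. It does not: the ANOVA and the two improvement proportions need a change. Limited room to improve is a different and milder matter than false success.
- **The PTA is not the only gate.** A dome-shaped tumor at least 2 mm high and 5 mm wide, pointed out to the subject by staff, is unlikely to be self-graded as not visible. Baseline SSA 0 should be very rare, so the Clear proportion is barely touched. Baseline SSA 1 is the realistic case, and it should be uncommon. It is still not excluded, since the SSA is the subject's own perception recorded independently of the physician.
- **The large losses need a large f.** Power of 0.52 requires 30% of such tumors to be self-graded 0 or 1. Nothing in the documents supports a value that high, or any other value.
- **The direction is conservative.** A reader might infer that unearned successes favor active gel. The Visit 2 grade precedes treatment in a randomized, double-blind trial, so these tumors balance across arms on average. What remains is dilution and some noise from chance imbalance.
- **Baseline description is partly planned.** Section 9.3.4 provides for descriptive statistics on Visit 2 data and baseline severity. An SSA table would fit there, though the SSA is not named.

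None of this supplies the missing baseline condition.

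**Conclusion.** The gap in the text is clear: PTA, shape and size gate entry, the SSA does not, and the SSA Clear and Clear/Almost Clear proportions carry no baseline condition. The consequence is confined to those two supporting analyses of a secondary endpoint: higher rates in every arm, a difference scaled by (1 − f), and rates that cannot be read against the PTA rates. It is not a bias toward active, and it leaves the primary endpoint untouched.

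The size depends on f, which the documents do not give. Under the assumed rates and correlation the power loss is about 2 points at f = 2% (0.964 to 0.945), about 5 at 5% (0.962 to 0.908) and about 13 at 10% (0.96 to 0.83). The entry criteria make the low end plausible. The figures also assume that tumors starting at 0 or 1 stay there. Confidence is high on the wording and low on the size. Severity: minor.

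**What to change.** In 9.3.5.3 and the matching synopsis text:

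1. Run the SSA Clear and Clear/Almost Clear analyses on tumors with Visit 2 SSA of 2 or more. Alternatively, keep all tumors and count success only with at least a 1-grade fall from Visit 2. The alternative removes the false successes, but tumors that start and stay at 0 or 1 remain in the denominator as failures, so the difference is still scaled by (1 − f).
2. Run the SSA 2-grade improvement analysis on tumors with Visit 2 SSA of 2 or more, and the 1-grade analysis on those with Visit 2 SSA of 1 or more.
3. Report by arm the number of tumors below each floor.

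The change should be made before unblinding, so that the denominator cannot appear to have been chosen from the results. The Visit 2 SSA is already collected before randomization (6.2.2), so the restriction preserves the randomized comparison and needs no new procedure. The cost is slightly fewer tumors in the SSA dichotomies; if f proves to be near zero, almost nothing changes.
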